October 8, 2019

**A Prospective, Randomized, Double-Blind, Placebo-controlled Pilot Study of
Single-dose Intraoperative Ketamine for the Prevention of Delirium in
Otolaryngeal Cancer Surgery Patients**

NCT03040024

Date: October 8th, 2019

October 8, 2019

**Study Title: A Prospective, Randomized, Double-Blind, Placebo-controlled Pilot
Study of Single-dose Intraoperative Ketamine for the Prevention of Delirium in
Otolaryngeal Cancer Surgery Patients**

TABLE OF CONTENTS

1. Study Team.....	1
2. Abstract.....	2
3. Background and Significance.....	3
4. Objectives.....	4
5. Innovation, Impact & Leverage.....	4
6. Approach.....	6
7. Participant Selection.....	7
8. Procedures.....	8
9. Risks.....	10
10. Statistical analysis.....	11
11. Confidentiality.....	12
12. Literature.....	13
APPENDIX A- Study Flowchart and Schedule of Assessments.....	15
APPENDIX B- Study worksheets.....	16
1. CAM-ICU Worksheet	
2. The Cognitive Failures Questionnaire	
3. Mini-Mental State Examination (MMSE)	
4. Pain Scale	
5. Provider Instructions-Emory University Hospital Midtown (EUHM)	
6. Mini-Cog	
7. Richmond Agitation Sedation Scale (RASS)	
8. STOP-Bang Scoring Tool, Sleep Apnea Questionnaire	

Study Title: A Prospective, Randomized, Double-Blind, Placebo-controlled Pilot Study of Single-dose Intraoperative Ketamine for the Prevention of Delirium in Otolaryngeal Cancer Surgery Patients

Short Title: Delirium Prevention with Ketamine in ENT patients

Winship EU3268-16

1. Principal Investigator: [name]

Assistant Professor

Department of Anesthesiology

2. Abstract

The goal of this prospective randomized double blinded placebo controlled study is to investigate if a single dose of ketamine in addition to standard anesthesia will reduce the risk of delirium in otolaryngeal cancer patients postoperatively. Ketamine's effect on post-operative pain and opioid use will be measured as well. Electroencephalogram (EEG) will be utilized during the surgical procedure to evaluate its potential as a possible predictive device for delirium. The study will be a single center study at Emory University Hospital Midtown (EUHM).

Up to 100 patients will be consented in order to achieve at least 60 patients who will be randomly assigned and administered 0.5 mg/kg, 1mg/kg or placebo intravenous bolus after induction of anesthesia. A processed EEG device (SEDline, Masimo Corporation) will be used to gather raw EEG data for off line analysis among patients developing post-operative delirium. Patients will be screened for delirium with the CAM-ICU once per shift (3 times daily) for three days postoperatively. Currently, the CAM- ICU is performed by ICU nursing and documented in the electronic medical chart. Both CAM-ICU screens and SEDLine monitoring are part of the usual and customary practice associated with these cases at EUHM and it would be unusual for a case such as this to be performed without this clinical data. Pain will be assessed according to hospital protocol and postoperative opioid consumption will be determined from the medical charts.

Preoperative and postoperative cognitive assessment will be completed at the ENT clinic preoperative, and postoperative follow up visit (done by research assistant). Adverse

effects (e.g., hallucinations or nightmares) will also be evaluated for three days postoperatively.

Chart review, data collection/entry will be done by [name], research assistant and the research staff.

3. Background and Significance:

Delirium is a frequent post-operative complication of major surgery with a reported incidence of 10-70 % [1] [2] [3]. After major head and neck cancer surgeries the incidence of delirium is reported to be over 25% [3]. Delirium is associated with increased morbidity and mortality, prolonged length of hospital and intensive care unit (ICU) stay and functional and cognitive decline [4] [5] [6] [7]. A history of dementia or depression, chronic medical illness, male gender and age>60 years are consistently described as risk factors for delirium [8] [9]; in the head and neck cancer patient population length of surgery and alcohol consumption have been identified as well [3] [10]. Currently there is no effective prophylactic treatment for delirium identified. Even the treatment of delirium remains difficult [11]. A Cochrane review on delirium prevention in hospitalized patients came to the conclusion that there is a paucity of research in this area resulting from difficulties in delirium detection and confounding factors like pre-existing cognitive impairment or multiple medical problems [12].

Recently a small randomized trial in cardiac surgery patients found a significant reduction in postoperative delirium (31% to 3%) when sub-anaesthetic doses of ketamine (0.5mg/kg) were given upon induction [13]. The same group further published data for improved postoperative cognitive function with ketamine in cardiac patients [13]. A follow up randomized prospective study in cardiothoracic patients looking at ketamine and delirium is currently recruiting (PODCAST).

Ketamine's benefits are thought to be based on its NMDA antagonism, HCN1 inhibitory effects and its anti-inflammatory properties [14]. Multiple studies have shown decreased post-operative pain with decreased post-operative opioid use when ketamine was administered during the surgery [15]. Interestingly a recent study showed that a single dose of ketamine had a prolonged two week lasting effect on patients with refractory depression [16].

Ketamine is a drug that has been in use for more than half a century, is inexpensive and has a wide margin of safety.

We are proposing a prospective randomized placebo controlled study to elucidate the effects of ketamine on postoperative delirium in the head and neck cancer population receiving “flaps”, administered peri-operatively.

4. Objectives:

Primary Aim:

Optimize our intraoperative treatment protocol for head and neck cancer patients to reduce the incidence of delirium and associated postoperative cognitive dysfunction. The hypothesis is that ketamine decreases delirium postoperatively in this high risk surgical patient population.

Secondary Aims:

1. Determine the dose response relationship for intraoperative ketamine and delirium reduction. Our hypothesis is that higher dose ketamine will lead to a more profound reduction in postoperative delirium.
2. Determine if a single dose of ketamine will reduce post-operative pain and opioid requirements. Our hypothesis is that the higher dose of ketamine will lead to a more profound decrease in objective pain scores.
3. Determine if raw EEG data can predict postoperative delirium during general anesthesia. Our hypothesis is that EEG patterns will correlate with incidence of post-operative delirium.
4. Evaluate length of ICU and length of hospital stay (done by medical chart review). Our hypothesis is that ketamine administration will not increase ICU/hospital stay.

5. Innovation, Impact & Leverage.

The successful completion of this study will provide critical data on a therapeutic and/or prophylactic effect of perioperatively administered ketamine on postoperative delirium. Delirium has been associated with increased length of ICU and hospital stay, increased cognitive impairment/decline and mortality. Despite increasing evidence of ketamine's ability to reduce postoperative delirium in cardiac patients, its opioid sparing effects and decreased postoperative opioid needs, ketamine is not widely used. Clinicians are concerned that psychoactive properties (e.g., hallucination and dissociative states)

interfere with post-operative cognitive function. These side effects however are rarely seen when ketamine is used in subanaesthetic doses.

Additionally, EEG data will be used to determine if this tool can be a possible predictor of delirium.

Currently, the most common way to monitor brain function during surgery is via processed electroencephalogram (EEG) monitors (SEDLine). These devices use frontal or fronto-temporal EEG electrodes, to measure the electrical activity of the brain. A special computer program translates these brain waves into a dimensionless number that roughly correlates to the dose of anesthesia administered. A purpose of our research is to utilize the electrical information from the raw EEG signals to determine if EEG patterns can predict a propensity to develop postoperative delirium. Our approach is to probe deeper into the analysis of the EEG signal than simply depth of consciousness by developing a taxonomy of specific states leading up to and through emergence.

EEG technology measures the electrical potential generated by synaptic input onto the dendrites of cortical neurons. Although higher frequencies are attenuated somewhat by the skull, a wide range of frequencies can be observed even with the abbreviated montage typical for the commonly available devices. With a minimal amount of effort the EEG file is available for download from the device via USB stick. The sensors are pre-packaged with gentle adhesive and applied to the patient's forehead while the patient is awake and removed with a minimal amount of discomfort (similar to a Band-Aid).

Although these EEG devices are not considered an ASA standard monitor for general anesthesia, many practitioners elect to place these sensors for routine cases as a monitor of depth of anesthesia. Several other benefits of these devices have been proven through the use of these devices and their utility as a standard monitor has been considered [17]. Previous experiments using abbreviated EEG records in this fashion have shown variations in the post-operative pain that correlated with their EEG patterns just before emergence from general anesthesia [18]. This is in contrast to the majority of the past studies using these devices that have focused on the predictive value of the number derived from the proprietary algorithm developed by the manufacturer. These algorithms reduce the EEG information into a single dimensionless number which roughly correlates with depth of anesthesia, although this concept has come under criticism. Our study involves quantitative EEG analysis of multiple electrodes placed over frontal brain regions of patients with co-morbid conditions. The value of EEG frequency

October 8, 2019

analysis in predicting delirium is unknown, but it has the potential to be an important tool in determining risk of delirium.

6. Approach:

Our aim is to optimize our perioperative treatment protocol for head and neck cancer patients in the operating room to positively impact ICU outcomes, by improving the incidence of delirium, associated postoperative cognitive dysfunction and pain control. This is a single center prospective randomized double blinded placebo controlled study that will be conducted at EUHM

Study arms:

1. 0.5mg/kg pre-incision bolus
2. 1.0mg/kg pre-incision bolus
3. Saline placebo pre-incision bolus

Standard general anesthesia will be applied with following standardized drugs:

Sevoflurane, fentanyl, hydromorphone, succinylcholine, rocuronium, cis-atracurium, lidocaine, propofol. Dosing and choice of above medications is at the discretion of the anesthesiologist.

Primary Outcome:

Delirium (measured by Confusion Assessment Method for Intensive Care Unit criteria, CAM-ICU) Measurements: Prior to surgery (baseline assessment upon study enrollment in ENT clinic) and postoperative days 0-3 (afternoon/evening on postoperative day 0, POD 1-3 measurements per shift as per Emory delirium protocol)

Secondary Outcomes:

1. Pre- and postoperative cognitive dysfunction (assessed in ENT clinic at pre- and post-operative visits or at anesthesia preoperative clinic) with the Mini-Cog, Mini-Mental Status Examination (MMSE) and the Cognitive Failure Questionnaire (CFQ).
2. Pain assessment (Prior to surgery (baseline assessment upon study enrollment in ENT clinic) and postoperative days 0-3 (afternoon/evening on postoperative day 0, and POD 1-3 per Emory protocol every 4 hours). Assessed by observer-based Behavioral Pain Scale or Behavioral Pain Scale (Non-Intubated) with subsequent administration of patient-reported Visual Analog Scale.

October 8, 2019

3. Post-operative use of narcotics (assessed POD 0-3 from medical chart)
4. Off line EEG analysis to correlate with postoperative delirium

7. Participant Selection

Inclusion criteria:

Inclusion criteria:

1. Patients 18 years of age and older, with otolaryngeal cancer receiving surgery with general anesthesia.

(Please note we are purposefully including patients with higher predisposition to delirium as we are investigating potential preventive strategies for this diagnosis of multiple etiologies. Patients at higher risk of delirium (e.g., advanced age, chronic hypertension) will be included in our study. Additionally, other common risk factors that exist in this patient population (e.g., alcohol or nicotine use) are thought to contribute to delirium postoperatively. [19])

2. Competent to provide informed consent.

Exclusion criteria:

1. Emergency surgery
2. Monitored Anesthesia Care (i.e., regional anesthesia alone without plans for general anesthesia)
3. Surgery involving the eye, eyebrow, forehead, or frontal scalp near the sensor placement
4. Poor health literacy (see next section)
5. Patients with an allergy, or have experienced any drug reaction to ketamine will be excluded.
6. Pregnant or lactating patients
7. Patients in active alcohol withdrawal
8. Patients with chronic pain who are taking buprenorphine

Subject Replacement

Subjects who are not admitted to the Intensive Care Unit after surgery, will be replaced, but will be followed per protocol through the final visit 2-6 weeks post-operatively.

Recruitment Plan/Eligibility Screening:

Patients undergoing surgical procedures requiring general anesthesia will first be approached for participation during the patient's preoperative visit, at the preoperative ENT clinic visit or on the day of surgery. A clinical research coordinator or other research personnel will be available to answer questions and obtain informed consent from the patient. It will be made clear to the patient that study participation is optional and that they can "opt out" at any time even if they have signed a consent form. In order to assure that our study participants are capable of understanding the information provided in the informed consent a single question screen will be used to detect inadequate health literacy: "How confident are you filling out medical forms by yourself?". This has been used in previous hospitals to detect poor health literacy [20]).

We intend on enrolling up to 100 male and female patients that meet eligibility criteria in order to have 60 patients who complete all study assessments. In addition to examining the potential effects of age, anesthetic drugs, and other patient and clinical factors on cognitive trajectories post-anesthesia, gender will be recorded and statistically examined as a potential contributor to different EEG patterns among our patients in this observational study.

8. Procedures:

- Upon enrollment, demographic data and medical history will be collected, subjects will be questioned about obstructive sleep apnea (OSA) using the STOP-Bang Questionnaire [21]). They will also be screened for cognitive impairment using Mini-Cog, Mini-Mental Status Examination (MMSE) and the Cognitive Failure Questionnaire (CFQ). A baseline pain assessment will be performed using the Visual Analog Scale. A baseline assessment of delirium will be obtained using the Confusion Assessment Method for Intensive Care Unit (CAM-ICU) criteria.
- Patients will be randomized to one of three groups on the morning of surgery by the Investigational Drug Service, before they enter the operating room. A randomization table will be provided and the subject assignment will be the next available number on the list. The study staff will be blinded to the list and the assignment. Group 1 will be given 0.5mg/kg of ketamine pre-incision as an intravenous (IV) bolus. Group 2 will receive 1.0mg/kg of ketamine pre-incision as

an IV bolus. Group 3. Will be administered saline/ placebo pre-incision an IV bolus. The provider will be blinded to the treatment assignment.

- Upon arrival in the operating room, before the induction of anesthesia, disposable EEG sensors (SEDLine) will be applied over the forehead according to the manufacturer's instructions.
- The pads will be placed out of the surgical field. For surgical cases where patient positioning or surgical skin preparation may interfere with good sensor contact, tape or Tegaderm® patches will be applied over the sensors to ensure they stay dry and in place.
- The patient will then be induced according to standard of care at the anesthesiologist's discretion. After induction a single bolus dose of ketamine (0.5mg/kg or 1mg/kg) or saline placebo will be given intravenously.
- The operation itself will proceed in the usual fashion using the standard monitors placed in all such cases according to institutional practice. Operative characteristics will be recorded.
- At the conclusion of the operation, the anesthesia practitioner will press the event marker button to aid in synchronizing the EEG raw data. The provider will adhere to specific guidelines (Provider Instructions), data will be recorded and the EEG file (without patient identifiers) will be downloaded and stored securely.
- The sensor will be removed and EEG data will cease to be collected before transport to the recovery room.
- While in the recovery room, the patient's pain level will be assessed (observer-based Behavioral Pain Scale or Behavioral Pain Scale (Non-Intubated) with subsequent administration of patient-reported Visual Analog Scale) as standard of care. The patient will be screened for post-operative delirium using the CAM-ICU delirium score and the Richmond Agitation and Sedation Score (CAM-ICU; RASS) 30 minutes after arrival and at discharge.
- While in the ICU pain assessment will be performed on postoperative days 0-3 (afternoon/evening on postoperative day 0, and POD 1-3 per Emory protocol, that is typically recorded by staff every 4 hours). Assessed by observer-based Behavioral Pain Scale or Behavioral Pain Scale (Non-Intubated) with subsequent administration of patient-reported Visual Analog Scale. Available data will be

gathered from the medical chart including vasopressor use, ICU and hospital length of stay.

- The patient will be screened for post-operative delirium using the CAM-ICU delirium score and the RASS during the ICU stay, typically recorded three times a day per Emory SOC. Available data will be gathered from the medical record for POD 1-3.
- At the routine outpatient ENT clinic postoperative visit that may occur from 2 to 6 weeks after surgery, cognitive impairment again will be screened with the Mini-Cog, Mini-Mental Status Examination (MMSE) and the Cognitive Failure Questionnaire (CFQ). Pain assessment will be performed using the Visual Analog Scale.
- This will be done by our research assistant.
- Post-operative use of narcotics will be assessed POD 0-3 from medical chart and at postop clinic visits at the ENT clinic visit postoperatively. The subject's study participation will end at the postoperative ENT clinic visit. 30 day readmissions, as well as mortality will be captured.

9. Risks

a. Risks regarding EEG sensors:

There is a very small chance of minor skin irritation from applying sensor strips (as the conductive gel has a minimal amount of latex-free adhesive similar to EKG leads); these skin reactions typically go away in 30 minutes without treatment. There is no more risk of skin irritation or discomfort from application or removal of these sensors than occurs during the removal of a Band-Aid. It should be noted that SEDLine sensors are routinely placed on the forehead of surgical patients without adverse effects. However, an information sheet with general instructions on care for minor skin problems after sensor removal will be made available. This sheet will also have recommendations for recognizing and treating minor skin irritation (i.e., mild soap and water) and the contact information for the study coordinator.

b. Risks regarding ketamine are as follows:

According to the manufacturer the anesthesia induction dose is as follows: the initial dose of ketamine administered intravenously may range from 1 to 4.5 mg/kg. The average amount required to produce 5–10 min of surgical anesthesia has been 2 mg/kg. The short-term side effects of ketamine at higher doses (>1–2 mg/kg) than the dosages proposed for this study (0.5 or 1 mg/kg) include tachycardia, nystagmus, hypersalivation, euphoria, emergence reactions, hallucinations and nightmares [22] In the doses used in this study (low dose ketamine at 0.5 and 1mg/kg after induction), it is very unlikely that these side effects will happen. [23]

c. ADE reporting and Data Safety Monitoring Plan:

The Emory School of Medicine, section of Anesthesiology Research, will conduct this study according to the national rules, regulations and guidelines governing human clinical research. In addition, procedures cited by the US Code of Federal Regulations (Title 21) will be followed as these apply to the principles of Good Clinical Practices and approval by the Emory Institutional Review Board (IRB). Investigators will complete Emory University required research training. All individuals involved in the study and data collection will be made aware of the unanticipated event reporting policy.

The research team will monitor subjects randomized and treated in the study for adverse events related to the research through the final study visit in the ENT clinic. If the change from baseline is considered by the investigator to be part of the normal fluctuations of an underlying disease process, this shall not be reported as an adverse event (AE). If the change in baseline is considered by the investigator to be an untoward medical occurrence different from the standard of care, this medical occurrence shall be reported as an AE. Any event meeting serious adverse event criteria will be reported by the research team immediately to the PI via email or telephone and will be reported to the Institutional Review Board (IRB) per policy. The PI will also inform all investigators of the event via email. The common grading system will be used for adverse event reporting where Grade 1 is mild, Grade 2 moderate, Grade 3 severe, Grade 4 life-threatening or disabling, and Grade 5 death related to AE. Should emergency unblinding be required for the safety of the patient, the PI will contact the Investigational Drug Service responsible for the preparation and dispensing of the study medication.

October 8, 2019

All enrolled subjects will be followed and monitored per Emory standard of care for postoperative surgery. Subject data will be evaluated on an ongoing basis during the study visits to ensure continued subject safety. There will be no pre-specified formal stopping rule for safety. An interim safety analysis will be performed after 10 participants are enrolled in each arm to ensure ongoing subject safety.

This monitoring plan is appropriate, since ketamine, an anesthetic drug, has an excellent safety profile and is commonly used in anesthetic practice. In addition, the doses used in this study are unlikely to cause major or minor side effects (e.g., emergence reactions, hallucinations).

10. Statistical analysis

a. Sample size:

It was assumed about 30% delirium incidence in our population by standard care [1] [2] [3].

Estimating 5-8 oropharyngeal cancer surgeries per week with a conservative enrollment rate of 50%, we will be able to recruit 130-208 patients in 12 months. We plan to enroll about 85 eligible patients in order to achieve 20 completed patients in each randomized group. For this pilot study, with this sample size we will have 85% statistical power under significant level of 0.05 to detect delirium incidence rate drop at least 30% (placebo) to 5% (two treatment arms combined) by one-sized Mantel Haenszel test, and such effect size is supported by an existing trial [13].

b. Data analysis:

For primary aim, the incidence of delirium will be calculated in each of three randomized group with 95% confidence interval (CI), and compared between each ketamine treated group with placebo group through Fisher's exact test. For secondary aims, the dose response effect of ketamine on delirium reduction will be tested by Cochran-Armitage trend test. For other outcomes, such as pain (and/or change from baseline), MMSE (and/or change from baseline), EEG data, length of stay (LOS), and use of narcotics will be first described by summary statistics (mean, median, standard deviation, frequency, and etc.) by three randomized groups and then compared by Chi-square test/Fisher's exact test, ANOVA, or Krusal-Wallis test wherever appropriate. The analysis will be

conducted by the Biostatistics and Bioinformatics Shared Resource at Winship Cancer Institute.

The Winship OnCore system will be used for data entry and analysis.

11. Confidentiality

The privacy of the research subjects will be ensured through standard procedures for securing research data. Whenever possible, a study number, rather than a name, will be used on study records. Identifying information will not appear when we present or publish the study results. All interactions with subjects during the study will occur in a private setting. Only Emory owned computers will be utilized to store data with any identifiers and these are compliant with the Emory disc encryption policy.

12. Literature:

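### Aim 4 tests a no-harm hypothesis on plain length of stay with no rule for death or readmission, so an early in-hospital death can count as a short, favourable stay

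*Combined protocol and SAP*

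**What the plan says.** Section 4, Secondary Aim 4, sets the task: "Evaluate length of ICU and length of hospital stay (done by medical chart review"). The hypothesis follows: "Our hypothesis is that ketamine administration will not increase ICU/hospital stay". No margin is given.

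Under section 8, the ICU data are to be "gathered from the medical chart including vasopressor use, ICU and hospital length of stay". The same section later adds: "30 day readmissions, as well as mortality will be captured". The 30-day window is attached to readmissions, and no separate window is given for mortality. Section 8 also says: "The subject's study participation will end at the postoperative ENT clinic visit". That visit falls 2 to 6 weeks after surgery.

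In section 10b, "EEG data, length of stay (LOS), and use of narcotics will be first described by summary statistics" by randomized group. The groups are then compared using a list of tests that ends "ANOVA, or Krusal-Wallis test wherever appropriate".

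No section defines when a stay starts or ends, how a death in hospital is scored, or whether days of a later admission count. Section 10b does not name deaths or readmissions, and neither is among the numbered secondary outcomes in section 6.

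**The concern.** A hospital or ICU stay ends when the patient leaves or dies. Without a rule for death, a patient who dies soon after surgery contributes a small number of days, and small is the good end of this scale. If LOS means the index stay, a patient sent home early who then returns contributes only the first stay.

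The direction matters because Aim 4 is a no-harm hypothesis. An early death in a ketamine arm moves the comparison towards the hypothesis. Section 5 itself links delirium to both longer stay and mortality, so the two outcomes are not safely treated as unrelated. At stake is whether an Aim 4 result of no longer stay can be taken at face value.

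**Working it through.** **Plan's own figure.** The documents give no power, rate or expected value for LOS. Their one power figure, 85%, concerns delirium (30% versus 5%, 20 placebo versus 40 ketamine). It reproduces at 84.8% by exact enumeration of the one-sided Mantel-Haenszel test, but it does not bear on Aim 4.

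**Inputs.** From section 10a: 20 completed patients in each of 3 arms, so N = 60 and n = 20. Death rates, readmission rates and stay lengths below are assumptions.

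**1. Largest effect of one death in Kruskal-Wallis.** Suppose one death holds rank 1 (the shortest of all 60 stays) and is moved to rank 60 (worst).
- That patient gains 60 − 1 = 59 ranks. The 19 others in the arm each lose 1.
- Change in the arm's mean rank = (59 − 19)/20 = 2.0.
- Null SD of an arm's mean rank = √[(N + 1)(N − n)/(12n)] = √[61 × 40/240] = 3.19.
- Ratio = 2.0/3.19 = 0.63 null SD.

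This is the extreme case. A death that is not the shortest stay moves fewer ranks.

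**2. How likely is a death?** Assume 30-day mortality m of 1% to 3%.
- Any death among all 60: 1 − (1 − m)^60 = 45% to 84%.
- Any death in one given 20-patient arm: 1 − (1 − m)^20 = 18% to 46%.

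Both count deaths at any time to day 30. Only early in-hospital deaths shorten the stay, so the chance of the shift in step 1 is lower than 18% to 46% for a given arm.

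**3. Direction on the day scale.** Assume 20 patients in one arm who each stay 9 days. In the other arm, 18 stay 9 days and 2 die in hospital on day 3.
- Mean LOS: 9.0 versus (18 × 9 + 2 × 3)/20 = 8.4. The arm with deaths looks 0.6 day better.
- Days alive and out of hospital to day 30, with death scored 0: 30 − 9 = 21.0 versus (18 × 21 + 2 × 0)/20 = 18.9. The arm with deaths is 2.1 days worse.

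A simulation assumed lognormal stays (median 9 days, log-SD 0.5), no true effect on stay, and deaths on days 1 to 4. It gave the same directions:

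| Deaths in one arm of 20 | Shift in mean LOS (days) | Shift in days alive and out of hospital to day 30 |
|---|---|---|
| 1 | −0.4 | −1.0 |
| 2 | −0.8 | −2.0 |
| 3 | −1.2 | −3.0 |

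**4. Readmissions.** If k of 20 patients are readmitted for L days each, index-stay LOS omits kL/20 days per patient in that arm. This runs from 1 × 4/20 = 0.2 to 4 × 8/20 = 1.6 days. The comparison is affected only by the difference between arms. With L = 6, 3 readmissions against 1 gives (3 − 1) × 6/20 = 0.6 day. Equal counts of equal length give 0.

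**The case against.** The strongest reply is that LOS is not the trial's measure of death. Section 9c follows adverse events through the final visit, grades related death as Grade 5, sends serious events to the IRB, and plans an interim safety analysis after 10 participants per arm. Section 8 captures mortality separately. The section 10b list of other outcomes is open-ended and includes tests for proportions, so a table of deaths or readmissions by arm is not ruled out. A reader might infer that harm from ketamine would go unseen or be reported as benefit. The documents do not support that, because deaths remain visible through these other routes.

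A reader might also infer that the plan instructs that deaths be scored as short stays, or limits LOS to the index admission. It states neither; both follow only from reading plain LOS without a rule. Nor do the documents show that a death on day 3 would rank among the shortest. They give no distribution of stays, and section 7 keeps following patients who never enter the ICU, whose ICU stay would be zero. Deaths after discharge do not shorten the index stay, late in-hospital deaths may lengthen it, and deaths in the placebo arm push the comparison the other way.

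All of this limits the size. None of it repairs the LOS comparison. Nor would dropping such patients. Appendix A places LOS collection under the clinic-visit column, and section 7 counts patients who finish every assessment. If someone who dies before that visit is left out as a non-completer, the death simply disappears from Aim 4.

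**Conclusion.** The point holds in a limited form. Aim 4's no-harm hypothesis rests on an outcome with no rule for death or readmission, and an early in-hospital death in a ketamine arm would move that outcome the favourable way. The size is modest: at most 0.63 null SD of an arm's mean rank for one death, given 20 patients per arm. Actual distortion depends on event counts and stay lengths that the documents do not give.

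It would be tempting to quote the 45% to 84% figure as the chance that Aim 4 is distorted. It is the chance of any death to day 30 in any arm, on assumed mortality, and not of an early in-hospital death in a ketamine arm. It would also go too far to say that LOS should be reduced to description, since Aim 4 asks about stay itself.

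This is a secondary aim of a 60-patient pilot. The change is worth making because it is cheap and uses mostly data already planned, but the trial does not depend on it. It does not settle a separate limit: with no margin, a non-significant difference does not show that stay is not increased, whichever outcome is used.

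**What to change.** In section 10b:

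1. Keep ICU and hospital LOS as the Aim 4 outcomes, and define the start and end of each and whether LOS means the index stay.
2. Name Kruskal-Wallis as the LOS test and give in-hospital deaths the worst rank.
3. Add days alive and out of hospital to day 30 by arm, with death by day 30 scored 0 and readmission days subtracted.
4. Tabulate deaths and 30-day readmissions by arm, and state the window for mortality.

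**Cost.** Death dates and readmission dates must be abstracted from the chart. Because the last visit can fall as early as 2 weeks after surgery, the plan must say how day-30 status is obtained for patients whose visit comes before then. Readmissions to other hospitals may be missed unless patients are asked about them.
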